#### ACRONYMS AND ABBREVIATIONS

AE	Adverse Event
AIDS	Acquired Immune Deficiency Syndrome
ANC	Antenatal Care
ART	Antiretroviral Therapy
CHCT	Couple HIV Counseling and Testing
COVID	Coronavirus disease
CRF	Case Report Form
FTC/TDF	Co-formulated Emtricitabine-TenofovirDisoproxil Fumarate
HIV	Human Immunodeficiency Virus
HIVST	HIV Self-testing
HTS	HIV Testing Services
IDI	In-depth Interview
IRB	Institutional Review Board
IPV	Intimate Partner Violence
KCCA	Kampala Capital City Authority
MU-JHU	Makerere University – Johns Hopkins University Research Collaboration
OR	Odds Ratio
PMTCT	Prevention of Mother-To-Child HIV Transmission
PrEP	Pre-Exposure Prophylaxis
RA	Research Assistant
RCT	Randomized Controlled Trial
REDCap	Research Electronic Data Capture
SAE	Serious Adverse Event
SOC	Standard of Care
VCT	Voluntary Counseling and Testing
WHO	World Health Organization

#### SUMMARY

Uganda has the fifth highest HIV burden globally and one of the highest fertility rates in Africa. Prevention of mother-to-child HIV transmission Option B+ (PMTCT B+) is national policy in Uganda. To maximize the prevention and clinical benefits of PMTCT B+, the challenges of low HIV testing by male partners and high rates of post-partum discontinuation of antiretroviral therapy (ART), insufficient adherence, and incomplete viral suppression need to be addressed. Women may be more likely to continue ART long-term and have higher adherence post-partum if their partner is tested, there is mutual disclosure of HIV status, and their partner takes ART or PrEP, depending on his status. Innovative approaches are needed to allow men to test in settings other than busy antenatal clinics, preferably where they have privacy, are comfortable and do not miss work. Innovative HIV testing technology – HIV self-testing (HIVST) could increase male partner engagement in HIV testing, and uptake of prevention and care services through linkage to highly effective pre-exposure prophylaxis (PrEP) and ART for all HIV-positive men. This study has been designed to address this gap through an enhanced PMTCT B+ program with HIV self-testing, and linkage to PrEP or ART, for male partners.

In a demonstration project we recently completed among mutually disclosed East African HIV serodiscordant couples (the Partners Demonstration Project), integrated ART and PrEP delivery with time-limited PrEP for the HIV-negative partner as a 'bridge' until the HIV-positive partner was on ART for six months, and achieved viral suppression, was very acceptable, achieved very high uptake and adherence to ART and PrEP, and nearly eliminated HIV transmission. This protocol builds on that demonstration project by evaluating whether PMTCT outcomes are improved by increasing uptake of HIV testing and PrEP among HIV-negative men whose pregnant partner is HIV-positive. PrEP for HIV-negative male partners of HIV-positive pregnant women provides highly effective prevention benefits during an important 'season of risk' when men may have higher HIV acquisition risk from their partner if she is viremic (during the first few months after ART initiation, post-partum ART discontinuation or due to viral resistance), or from outside partners.

We will conduct a randomized trial to evaluate whether provision of oral HIV self-test kits to HIVpositive pregnant women overcomes male partners' reluctance to be tested in PMTCT clinics. Pregnant women will be trained in the use and interpretation of HIVST and given two oral fluidbased HIVST kits to use with or give to their partners, along with information about HIV testing and prevention and care services. We will offer men confirmatory testing regardless of their HIV test result through HIVST, counseling, and if negative, PrEP and if positive, ART. We will provide counseling to minimize social harms of HIV self-testing, and additional counseling and referral to social support services when social harms occur. This project will address key challenges in PMTCT B+ programs, by evaluating innovative strategies to increase male partner involvement coupled with offering PrEP to HIV-negative men, ART to HIV-positive men, and encouraging postpartum ART continuation and adherence among HIV-positive women.

Design:	Randomized clinical trial Up to 12 months of post-partum follow-up
Population:	HIV-positive pregnant women in Kampala, Uganda who have a male partner of unknown HIV status (approximately 500 women in total)
Study Sites:	Infectious Diseases Institute (IDI) Kasangati and collaborating antenatal care (ANC) clinics in Kampala, Uganda

Approach: We will recruit HIV-positive women ≥18 years accessing PMTCT B+ programs in Kampala, who have a male partner of unknown HIV status. Women will be randomized to the intervention (HIVST) or the control arm (invitation letters to deliver to partners to come to the ANC clinic where she receives care or IDI Kasangati for HIV testing). Women will be instructed in the use and interpretation of HIVST and be provided two HIVST kits to give to or use with their male partners. We will recommend that HIV-negative men use PrEP until their partner has been on ART for at least 6 months, and that HIV-positive men take ART. Specifically, PrEP as a bridge to ART will be offered to HIV-negative male partners as follows: when the HIV-positive pregnant partner is not yet taking ART, PrEP will be offered, and when the HIV-positive pregnant partner initiates ART, PrEP will be provided for the HIV-negative male partner for six months (i.e., when viral suppression in the HIV-positive partner would be expected to be typically achieved). This bridge to ART approach is detailed in Figure 1.

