#### Study screening

Women will be enrolled and followed at collaborating ANC clinics. Trained research staff will counsel potentially eligible women about the benefits of male partner testing, post-partum ART persistence, and possible participation in the study. Counseling messages will include:

Reasons for male partners to be tested for HIV:

- To know his status.
- If he is infected that he does not infect others.
- If he is positive, to help him to access care and treatment which will help him stay healthy longer.
- If he is negative, to help him stay HIV negative.
- To strengthen their relationship.
- To avoid testing by proxy since about half the time, he will have a different status than his partner.

HIV status disclosure:

- Does your partner know your status?
- If no, and you are positive, what do you think might happen if you discuss this with your partner?
- Where would you tell him? When would you tell him?
- Encourage women to tell him a story about the antenatal clinic, how other women have encouraged their partners to test for HIV, which has been beneficial for the family by keeping both partners health longer and see what kind of reaction he has.
- Importance of talking about HIV together with their partner so they can plan for the future.
- Risk of HIV for their children.
- Explore the possibilities of being sent away, relationship ending, violence, etc.

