## Table 3. Sample size calculations for comparison of proportion of

Randomization is 2:1 for Enhanced: SOC. Assumes 95% retention, 80% PrEP uptake

Assuming PrEP uptake in HIV-negative men is 80% and 60% of the men are HIV-uninfected, with a sample size of 500 we would have almost 90% power to detect an increase in PrEP use resulting from a change from 30% to 55% in test uptake. With 500 women, the power for assessing an increase in HIV test uptake exceeds 95% across a range of assumptions in Table 3.

Aim 2: Under the range of assumptions for HIV testing uptake in Aim 1, the overall HIV test uptake will be in the range 43-53% (Table 4) and the number of enrolled women with partners who test and begin ART or PrEP ranges from ~150-200. Assuming power for the causal inference can be approximated by logistic regression, we would have ~80% power to detect an OR of 1.75 or higher, assuming women have 50% ART continuation and viral suppression when male partners do not initiate PrEP or ART. If the number of women with partners who test is between 220-270, we would have approximately 85% power to detect an OR of 1.75.

Table 4. Power approximation for assessing impact of partner PrEP/ART use on women's viral suppression					
Overall HIV	HIV prevalence	HIV+ men on ART	Not on ART		

Overall HIV	HIV prevalence	HIV+ men on ART	Not on ART		
test uptake	in male partners	or HIV- men on	or PrEP		
		PrEP		OR=1.75	OR=2.0
43%	0.4	147	353	78%	92%
47%	0.3	166	334	81%	94%
50%	0.4	170	330	80%	94%
53%	0.3	189	311	83%	95%
Randomizatio	on is 2:1 for Enhance	ed: SOC. Assumes 95	% retention, 80	% PrEP upta	ke and

50% ART persistence

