3.3. Randomization

HIV-positive pregnant women are randomized in a 2:1 ratio to provision of HIVST kits to use with their male partners or to take an invitation letter to their male partner to be tested at their ANC clinic, or if the male prefers. Randomization was open label, with variable size blocks, without stratification.

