7. ANALYSES

7.1. General Considerations

Inferential statistical tests will be two-sided and will be performed at alpha levels of 0.05 and 0.10 to declare the significance of main effects and interaction effects, respectively.

No adjustment for multiplicity are planned.

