Descriptive analysis:

- We will tabulate the number of women by the their partners disposition: 1) No partner enrolled 2) Partner enrolled, not initiated PrEP/ART, 3) partners enrolled and have initiated PrEP/ART. Baseline demographic and risk characteristics of women will be compared by group. If Group 2 is less than 10% of the cohort, it may be combined with Group 1.
- We will describe the characteristics of the women's viral load at 12 months within each group: mean, median, IQR, proportion with suppressed viral load.

Statistical analysis:

We will use modified Poisson regression with robust standard errors to compare the proportion of women who are virally suppressed between groups.

The analysis will include men who were on ART at enrollment.

This comparison is not protected by randomization therefore we will adjust for the following potential confounders:

- Age (in categories)
- Viral suppression at baseline
- Trimester of pregnancy at enrollment

30 Sep 2021

- Randomization arm
- Baseline covariates that demonstrate imbalance between the groups ($p < 0.05$ in comparison of characteristics), not thought to be mediators of differences in outcome.
- Assessments occurring prior to April 2020 (prior to COVID 19)

We will assess for effect modification by analysis of interaction between the subgroups of women who are virally suppressed at enrollment.

Handling of missing VL data:

- If 12 month VL is missing, but VL is available from 9 month PP, the 9 mo VL will be used to estimate the 12 mo VL.

7.3.5. Aim 2b. Assess whether having a male partner who has initiated PrEP/ART affects viral load suppression at 6 and/or 12 months post-partum in his female partner

Endpoint: Viral suppression at the 6 and 12 month visit post partum.

Statistical analysis:

Repeated measure analysis will be used for this aim. The viral load at 6 month and 12 months will use a time-dependent covariate for whether her male partner had initiated PrEP/ARV at least 3 months prior to the VL measurement. We will assess whether initiation of PrEP/ARV 3 month prior increases the probability of viral suppression using GEE logistic or modified Poisson regression

Handling of missing VL data:

- If 12 month VL is missing, but VL is available from 9 month PP, the 9 mo VL will be used to estimate the 12 mo VL.
- If 6 month VL is missing, but VL is available from 3 month PP, the 3 mo VL will be used to estimate the 6 mo VL.

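### The non-randomised Aim 2 analyses do not name the enrolling antenatal clinic as an adjuster, so differences between clinics could pass for an effect of the partner's PrEP or ART

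*Protocol*

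**What the plan says.** The protocol's summary lists the sites as "Infectious Diseases Institute (IDI) Kasangati and collaborating antenatal care (ANC) clinics in Kampala, Uganda"; the number of clinics is not given. Under Study screening it states: "Women will be enrolled and followed at collaborating ANC clinics". Men are tested and offered PrEP at the partner's antenatal clinic or at IDI Kasangati (Partner invitation group; Male partner procedures; PrEP adherence). HIV-positive men are treated by local HIV care providers or at IDI Kasangati (Procedures for HIV-positive men).

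For Aim 2a, SAP 7.3.4 specifies: "We will use modified Poisson regression with robust standard errors to compare the proportion of women who are virally suppressed between groups". It then says: "This comparison is not protected by randomization therefore we will adjust for the following potential confounders". The list is age, baseline suppression, trimester, randomisation arm, assessment before April 2020, and any baseline covariate that differs between the exposure groups at p < 0.05 and is not thought to be a mediator. SAP 7.3.5 (Aim 2b) describes a repeated-measures model and gives no covariate list.

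Clinic is not named in either section. It is also absent from the baseline variables in SAP 5.2.1 and 6.3.1, the covariates in SAP 7.4.1, and the confounders in the protocol's Statistical considerations. No analysis uses it as a covariate, stratum or cluster.

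**The concern.** Aim 2 groups women by what their partner did, so adjustment is its only protection. Clinic could plausibly act on both sides of the comparison. On the exposure side, the protocol's background names staff attitudes and antenatal clinics that turn men away as barriers to male involvement, and flexible hours and faster processing as facilitators. These are features of a facility. On the outcome side, women's ART counselling, refills and visits take place in routine clinic care.

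If clinics that bring in more men also keep more women suppressed, the pooled comparison shows better suppression among women with treated partners even when the partner's treatment does nothing. SAP 2.2.1 lists Aim 2a among the primary endpoints. The inverse-probability weighting and exploratory instrumental-variable analysis in the protocol's Statistical considerations do not appear in the SAP, which leaves the covariate list to carry the whole burden.

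**Working it through.** **The plan's own figure first.** Protocol Table 4 gives Aim 2 power for OR 1.75 and 2.0, with 50% suppression in the unexposed and 95% retention. For the 147/353 row at OR 1.75:

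- p1 = 1.75/2.75 = 0.636, p0 = 0.50; group sizes 147 × 0.95 = 139.65 and 353 × 0.95 = 335.35.
- Pooled SE = 0.0502; unpooled SE = 0.0490.
- Power = Φ[(0.1364 − 1.96 × 0.0502)/0.0490] = Φ(0.775) = 78%, as stated.

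All eight cells reproduce within 2 points (78.1/92.2, 80.8/93.7, 81.2/94.0 and 83.0/94.9%). No stated figure is wrong; the issue is an omitted covariate.

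**Inputs for the illustration.**

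- From the documents: 500 × 0.95 = 475 women; 34% exposed (170/500, a Table 4 row); two-sided 0.05 (SAP 7.1); 50% suppression (Protocol, Sample size) or about 90% (Protocol, PMTCT B+ in Uganda).
- Assumed: two equal clinic groups, the gaps between them, and no true effect. The documents give no rates by study clinic.

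**Formula.** With uptake e1, e2 and suppression s1, s2 in the two groups:

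- P(suppressed | exposed) = (e1·s1 + e2·s2)/(e1 + e2)
- P(suppressed | unexposed) = [(1−e1)·s1 + (1−e2)·s2]/(2 − e1 − e2)

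Example, uptake 44% v 24% and suppression 60% v 40%: (0.264 + 0.096)/0.68 = 0.529 and (0.336 + 0.304)/1.32 = 0.485. RR = 1.09, OR = 1.20. The expected group sizes are 161.5 and 313.5, so SE = 0.0484, z = 0.92, and the chance of p < 0.05 is about 15%.

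| Uptake | Suppression | Exposed v unexposed | RR | OR | Chance of p < 0.05 |
|---|---|---|---|---|---|
| 39% v 29% | 55% v 45% | 0.507 v 0.496 | 1.02 | 1.05 | 5.6% |
| 44% v 24% | 60% v 40% | 0.529 v 0.485 | 1.09 | 1.20 | 15% |
| 49% v 19% | 65% v 35% | 0.566 v 0.466 | 1.22 | 1.50 | 55% |
| 54% v 14% | 65% v 35% | 0.588 v 0.455 | 1.29 | 1.71 | 80% |
| 44% v 24% | 95% v 85% | 0.915 v 0.892 | 1.03 | 1.29 | 12.5% |

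These figures leave out every other planned adjuster, so they are crude, upper-side values.

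**Does the remedy work?** Modified Poisson regression with robust standard errors was simulated under no true effect (475 women, 4 or 8 clinics, 1,000 runs per setting). Where uptake and suppression rose together across clinics, each with an SD of 5 or 10 points, omitting clinic gave RR 1.01–1.09 and type I error 7.3–16.6%. Where uptake did not vary between clinics, there was no bias (5.5–5.8%). With clinic as a fixed effect, RR was 0.99–1.00 and type I error 4.3–6.2% across all settings.

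**Would the imbalance rule catch it?** Suppose clinic were compared between exposure groups, with two groups of 237.5. Uptake of 39% v 29% gives z = 0.10/0.0435 = 2.30, which is flagged about 63% of the time. Uptake of 44% v 24% is flagged more than 99% of the time.

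**The case against.** The strongest reply is that the SAP already has a route for clinic. The imbalance rule in 7.3.4 is not limited to the variables in 5.2.1. Enrolling clinic is fixed at baseline and is not a mediator, and where the bias would be large the test would almost always fire. The protocol's confounder list is open-ended, and SAP 7.4.1 allows further covariates on a 10% change in estimate. Much is also common across clinics: trained research staff counsel, study staff perform the study procedures, and care follows national guidelines. Adjustment for baseline suppression would absorb part of any difference in clinic quality.

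Much of this stands, and it reduces the likely size. It does not close the gap. The rule acts only if someone compares clinic, and no list tells the analyst to do so. A significance test is unreliable for moderate differences. The rule is not stated for Aim 2b, and the 10%-change clause belongs to the disclosure models. Baseline suppression cannot reflect later differences in post-partum care.

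Two stronger readings are tempting. A reader might infer that men are treated mainly at their partner's own clinic. The documents do not say so: IDI Kasangati is an alternative throughout, and men's ART is placed with local HIV care providers or IDI Kasangati. A reader might also infer from "Randomization was open label, with variable size blocks, without stratification" that Aim 1 is confounded by clinic. It is not: allocation is random regardless of clinic, so omitting clinic there affects chance balance and precision only.

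**Conclusion.** The point holds for Aims 2a and 2b. Clinic could influence both the exposure and the outcome, and neither analysis names it. The size is unknown. Under the assumed gaps, and before the other adjusters, the spurious OR runs from about 1.05, which is negligible, to about 1.5–1.7, close to the OR of 1.75 the aim was powered for. Bias needs clinics to differ in both partner uptake and women's suppression. It favours the study hypothesis only if the two differences run the same way. The documents show neither, so they do not support a reading that the Aim 2 result will be biased, or biased in a known direction. What they support is that the plan neither adjusts for clinic by design nor provides a table from which a reader could check.

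**What to change.** - In SAP 7.3.4 and 7.3.5, prespecify the enrolling antenatal clinic as a fixed effect, pooling very small clinics by a stated rule.
- List clinic in SAP 5.2.1.
- Tabulate partner PrEP/ART initiation and women's suppression by clinic.
- In SAP 7.4.1, name clinic in the covariate list rather than leaving it to the 10%-change rule.

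The cost is SAP wording and some degrees of freedom; how many depends on the number of clinics, which is not stated. The change assumes that the enrolling clinic is recorded for each woman. That is likely, since women enrol there, but the documents do not confirm it.

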#### **Specific Aims**

# Aim 1: Determine whether an enhanced PMTCT program with HIV self-testing for male partners and provision of PrEP to HIV-negative male partners increases the proportion of male partners who test for HIV and men who initiate PrEP.

Innovations are needed to reach male partners for HIV testing that allow men to test where they are comfortable, which typically is not in busy antenatal clinics. Provision of HIV self-tests (HIVST) to pregnant women for their partners is safe, acceptable, and effective, and could facilitate partner testing, and increase uptake of PrEP by HIV-negative men and ART by HIV-positive men. HIVST is a promising approach to increasing partner and couples testing, which has not yet been evaluated in the context of PMTCT B+ programs. We will randomize 500 HIV-positive women initiating PMTCT B+ in Kampala in a 2:1 ratio to one of two partner testing strategies: 1) HIVST kits (intervention) to give to or use with their partner, or 2) invitation letters for fast-track testing at the clinic (standard of care). Men who test will be offered confirmatory testing and counseling. Men who test HIV-positive will be linked to ART, and men who test HIV-negative will be offered PrEP for the first six months after his partner initiates ART through PMTCT.

The co-primary outcomes are the proportion of male partners who test for HIV and the proportion of HIV-negative male partners who initiate PrEP.

# Aim 2: Evaluate whether HIV testing combined with PrEP and ART use among male partners increases effective post-partum ART use among HIV-infected Ugandan women in PMTCT B+.

Pregnant HIV-positive women may be more likely to continue ART after delivery and have higher adherence post-partum if their partners are tested, there is mutual disclosure of HIV status, and their partner takes ART or PrEP, depending on his status. We will evaluate ART use and viral suppression at 12 months post-partum among the 500 HIV-positive pregnant women who are randomized to male partner testing strategies (Aim 1). In this observational analysis, we will use causal inference methods to assess whether the outcome (women's viral load at 12 months post-

partum) is improved by the exposure (male partner testing and engagement in HIV care or prevention–PrEP use among HIV-negative men and ART use among HIV-positive men).

The primary outcome is viral suppression at 12 months, as a measure of the woman's effective ART use in the first 12 months post-partum and her adherence. Viral suppression will be defined as plasma viral load <400 copies/ml at 12 months post-partum. We will analyze the outcome (viral suppression in the female) by the male partner's testing outcome and PrEP use among HIV-negative men. Secondary outcomes include a) post-partum adherence, as measured by pharmacy records, which will be used to measure ART dispensation, and women's self-report about treatment interruptions; b) infant HIV status at 6 weeks as determined by PCR results (HIV infected/uninfected); and c) infant survival at 12 months as reported by the mother.

#### Aim 3: Assess the acceptability of HIV self-testing and PrEP, as well as perceptions of ART adherence and HIV status disclosure during the COVID-19 pandemic, to pregnant women taking part in PMTCT B+ and to their male partners, using qualitative and quantitative methods.

PMTCT B+ has the secondary benefit of reducing HIV transmission to male partners if HIV-positive women continue antiretroviral therapy (ART) long-term with high adherence. However, optimizing the effectiveness of PMTCT requires understanding factors that influence low uptake of HIV testing by male partners (~1/5 of partners of women in Uganda PMTCT programs are tested for HIV). In addition, previous studies have indicated that 1/3-1/2 of African women discontinue ART after delivery, and the importance of disclosure and partners' engagement in HIV care or prevention need to be assessed to determine how much those factors influence ART continuation post-partum. During the COVID-19 pandemic, both adherence to ART and initiation of status disclosure may be greatly impacted.

We will use quantitative and qualitative methods to investigate acceptability of HIVST and PrEP. Additionally we may explore the perceptions of COVID-19 and the intersections of HIV status disclosure, male partner testing, and access to and experiences of HIV prevention and treatment during the pandemic. Quantitative behavioral data will be collected from the study cohort during clinic visits using multiple validated questionnaires. A structured interview administered to all HIV-infected female partners at enrollment will ask about knowledge of the partner's HIV status, disclosure, fertility desires, relationship power, and intimate partner violence. Up to 110 individual interviews will be conducted. A purposefully selected subsample of up to 90 individuals will take part in qualitative in-depth interviews to achieve in-depth understanding of the acceptability of HIV self-testing and PrEP use by male partners to women in PMTCT B+ and to male partners. In a sample of 10 PMTCT providers, we will assess perspectives of HIVST, facilitated disclosure, male partner linkage to HIV care and prevention, and women's ART use post-partum.

The goal of the qualitative analysis is to assess the acceptability of HIV self-testing and PrEP use by pregnant women in PMTCT B+, their male partners, and implementation perspectives of PMTCT providers.

